Change in AIRQ™ score and control level between the initial telehealth visit and follow-up visit(s) (using the AIRQ™ 3-Month Recall when available) will be explored by site and cluster and presented using descriptive statistics (n, frequency, mean, and SD) and mean change of AIRQ™ by item and total score, (95% CIs computed; initial visit vs. follow-up visits) and a shift analysis for control level.

Change in AIRQ™ score and control level between the initial telehealth visit AIRQ™ (12-Month Recall) and follow-up visit(s) (using the AIRQ™ 3-Month Recall when available) will be stratified by site and cluster and presented using descriptive statistics (n, frequency, mean, and SD). Mean change of AIRQ™ by item and total score (95% CIs computed; initial visit vs. follow-up visits) and a shift analysis for control level will be conducted.

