5.3 Sample Size and Power Calculations

As the aim of this study is to assess the process and feasibility of implementing the AIRQ™ using a telehealth platform, inferential statistics will not be conducted, and a formal sample size estimation is not applicable. Each site will target approximately 50 patients; however, some sites may be able to recruit more than 50 patients, resulting in a total sample size of approximately 750 to 1,500 patients. Further, each cluster (primary care, specialist, novel) will

contain approximately 3 to 5 sites to have balanced sample sizes between the practice clusters. Implementing the AIRQ™, Asthma Checklist, and educational resources (PRECISION program) among approximately 50 patients will provide sites with enough experience to provide feedback on the outcomes, barriers, benefits, challenges, ease of implementation, and areas for improvement for future integration as a telehealth and in-person platform. Additionally, an adequate sample should be available to confirm the performance of the AIRQ™ in a diverse primary care cluster.

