2. STUDY DESIGN AND SAMPLE SIZE

This community program intervention study will examine the process of integrating the AIRQ®, Asthma Checklist, and educational resources (PRECISION program) into clinical practice using in-person or telehealth visits. Providers' use of patients' responses to the AIRQ®, Asthma Checklist, and educational resources to guide treatment and asthma work-up and management will be examined. All participants will be enrolled in the study by February 2022. Study duration for each site will be 12 months, including a nine month study implementation phase (starting when the last patient is enrolled at the site) and an additional three months of follow-up to assess the sustainability of using the PRECISION program in clinical practice (sustainability stage). The nine-month implementation stage will allow for potential follow-up visits for each enrolled patient. The three-month sustainability stage will allow for sites to continue to implement the PRECISION program in their clinical practice and for sites to describe any continued benefits of using the PRECISION program at their site.

Approximately 15 to 20 clinical sites will be recruited to participate in this study, categorized into the following practice clusters: (1) primary care site (e.g., private practice, FQHC; 2) specialty care site (pulmonary, asthma/immunology); and (3) novel sites (e.g., pharmacy, nurse practitioners, nurse educators, prescribers and non-prescribers, telehealth component of Allergy and Asthma Network).. Sites will be able to conduct in-person and telehealth visits for initial and follow-up visit(s).

During the clinic visit (telehealth or in-person), HCPs will assess the patients' responses to the AIRQ® questions, discuss the results with the patient, and use the Assess component of the Asthma Checklist (as appropriate per HCP judgment). Before completing the initial study visit, patients will be asked if they would be willing to complete additional questions and, for those who agree, sites will send them an electronic survey link (via YouGov) that will include the following questionnaires: the Asthma Clinic Experience (ACE) Questionnaire, [CCI](#)

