Sociodemographic Questionnaire. If a follow-up visit (telehealth or in-person) is conducted during the follow-up period, the clinical site will administer the AIRQ® three-month recall version (regardless of timing of follow-up visit). Sites/HCPs will complete a Clinical Case Report Form (CRF) after the initial visit and after the first follow-up visit (if conducted) for each participant. For the initial and first follow-up visit for which patients complete an AIRQ®, HCPs will be required to review the Assess component of the Asthma Checklist and provide their responses on the CRF; while sites are encouraged to use the AIRQ® for any additional follow-up visits during the study and to provide documentation of the AIRQ® scores, additional CRFs will not be completed by the HCPs.

Additionally, Evidera will host a 30-minute conference call with each clinical site for up to four timepoints (touchpoints) to discuss the implementation of PRECISION tools (i.e., frequency of visits to and the number of portable document format (PDF) file views from study website), assess whether sites are meeting their targets for using the telehealth platform, address site questions, and discuss any challenges of implementing the PRECISION program. These meetings will take place at Months 1, 2, 3 (optional), and 6 and will be used to identify any sites that may benefit from participating in a re-training session. The optional Month 3 touchpoint will be based on whether the site has any difficulties with the study.

Study Population: Clinic staff will invite patients age ≥ 13 years with an HCP-confirmed asthma diagnosis who present for a clinic visit (telehealth or in-person) to complete the AIRQ® and participant questionnaires. Each site will aim to recruit approximately 50 to 75 patients with a total sample size ranging from approximately 750 to 1,500 patients. The number of patients recruited from each site may be modified (i.e., able to recruit > 75 patients) to ensure that the target study sample size is obtained.

Inclusion Criteria: Patients must meet all of the following criteria to be eligible for enrollment:

1. ≥ 13 years of age at the time of enrollment
2. Prior diagnosis of HCP-confirmed asthma
3. Able to read, understand, and speak English or Spanish sufficiently to self-complete or be administered the AIRQ™ via telephone, desktop computer, or mobile device (e.g., smartphone, iPad)

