2.1 Sample Size Estimations

As the primary aim of this study is to assess the process and feasibility of implementing the AIRQ™, Asthma Checklist, and education resources (PRECISION program) using a telehealth or in-person platform, inferential statistics will not be conducted as part of the primary endpoint, and a formal sample size estimation is not applicable. Each site will target approximately 50 patients with asthma; however, all sites will be capped at 75 patients per site. This cap may be modified depending on individual site recruitment to ensure the targeted sample size is met. Implementing the AIRQ®, Asthma Checklist, and educational resources (PRECISION program) among approximately 50 patients per site will provide sites with enough experience to provide feedback on the outcomes, barriers, benefits, challenges, ease of implementation, and areas for improvement for future integration as a telehealth platform.

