3. ANALYSIS SET

- **All enrolled patients:** All enrolled patients who have completed the initial visit with the AIRQ®
- **Web-survey analysis dataset:** All enrolled patients who complete the initial visit and the web survey
- **Primary care cluster dataset:** All enrolled patients at a primary care site who complete the initial visit and the web survey **CCI**.
- **Exacerbation dataset:** Includes EMR or claims data for enrolled patients who completed the initial visit and have available pre-post exacerbation data.
- **Follow-up analysis set:** All enrolled patients who completed the initial visit with the AIRQ® and have at least one follow-up visit completed in the nine-month implementation period with the follow-up AIRQ®. Patients are not required to have a follow-up visit.
- **HCP analysis set:** All health care providers trained on the study who complete the post-study survey and/or qualitative interview

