AIRQ® score and control level at the initial visit and Follow-up AIRQ® score and control level at follow-up visit(s) will be explored overall and by practice cluster, and presented using descriptive statistics (n, frequency, mean, SD) (Table 4a, Table 10a and Table 10j). The change in AIRQ® between initial visit and first follow-up visit will be evaluated using paired t-tests for the overall sample, and by practice cluster (Table 15). If the sample size allows, change in AIRQ® score will also be evaluated based on elapsed time from initial visit to follow-up by groups (e.g., 0–3 months; 4–6 months; 7–9 months). In Table 16, shift analyses will be conducted to evaluate change in AIRQ® control score between the initial and first follow-up visit. The frequency of patients improving, maintaining or worsening in AIRQ® control level from initial to first follow-up visit will be described in Table 17. Similarly, shift analyses for AIRQ® control score between the initial and final follow-up visit will be presented in Table 18, and the frequency of patients improving, maintaining or worsening in AIRQ® control level from initial to final follow-up visit will be described in Table 19. If the sample size for additional AIRQ® completions after the first follow-up allows, an additional exploratory analysis will be to explore the trajectory of change in AIRQ® score in relation to visit number and other clinical variables.

Statistical analysis plan
D2287L00028 (EVA-26645)

AstraZeneca
27 Sep 2023

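### The paired t-tests of AIRQ change ignore site, so their p-values may be too small if changes correlate within site

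*SAP*

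**What the plan says.** For the secondary objective on AIRQ change, SAP 5.1.2 names one test. The change between the initial and the first follow-up visit "will be evaluated using paired t-tests for the overall sample, and by practice cluster (Table 15"). The shift tables and the improved/maintained/worsened tables in the same section name no test. Practice cluster means type of practice (primary care, specialty, novel; SAP 4.3), so splitting by it does not account for site.

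Patients are nested in sites. SAP 2 says "Approximately 15 to 20 clinical sites will be recruited to participate in this study", and the sites themselves run the program: "The three-month sustainability stage will allow for sites to continue to implement the PRECISION program in their clinical practice". On site size, SAP 2.1 says "Each site will target approximately 50 patients with asthma; however, all sites will be capped at 75 patients per site", and allows the cap to be changed. On follow-up, SAP 3 says "Patients are not required to have a follow-up visit". Protocol 5.3 expects each practice cluster to "contain approximately 3 to 5 sites to have balanced sample sizes between the practice clusters".

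Protocol 5.1.2 had site in view. There the change "will be explored by site and cluster and presented using descriptive statistics (n, frequency, mean, and SD"), with 95% CIs for mean change but no stated method for them. SAP 5.1.2 keeps the practice-cluster breakdown and carries over neither the by-site change nor the intervals. SAP 6.1 covers response bias and selective follow-up, not clustering. SAP Appendix B lists no change to the Table 15 test. The visible text contains no site term, mixed model, GEE, cluster-robust variance or ICC.

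**The concern.** The model behind the paired t-test is D_ij = μ + e_ij for patient i at site j, with all e_ij independent. If sites differ in how much their patients change, the model should be D_ij = μ + u_j + e_ij. Changes within a site are then correlated, and the ordinary standard error of the mean is too small for inference about sites in general.

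Taking differences removes site differences in level that are stable over time. It does not remove site differences in change, and the documents give reasons to expect some:

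- Sites are chosen partly for what each would bring to implementation (Protocol 3.1.1), and site-specific initiatives are expected (SAP 4.1.7).
- Re-training goes only to sites that may benefit from it (Protocol 6.1.2).
- Novel sites with several coaching sessions complete the follow-up CRF at the last session, while primary care and specialty sites do so at the first follow-up visit (SAP 4.1.4.2 and 5.1).
- The AIRQ may be self-completed or interviewer-administered (Protocol 4.1.2).

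At stake is how Table 15 is read. A change driven by a few sites could pass as a precise result for the program or for a practice type. Without the by-site display, the reader cannot see whether that happened.

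**Working it through.** **The plan's own figure.** SAP 2 gives a sample "with a total sample size ranging from approximately 750 to 1,500 patients". This reproduces as sites × patients per site: 15 × 50 = 750 and 20 × 75 = 1,500. The upper end needs the cap, since 20 × 50 = 1,000.

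**Inputs.** There are 15 to 20 sites overall and about 3 to 5 per practice cluster. Not stated, and therefore assumed: followed patients per site, m = 10 to 50 (follow-up is optional); site ICC of the change score, ρ = 0 to 0.10; and a two-sided 5% level, to match the protocol's 95% CIs. The SD of the change cancels.

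**Formulas.**
- Design effect: DEFF = 1 + (m − 1)ρ.
- Factor by which the CI should be wider: √DEFF.
- True size of the nominal 5% test: 2 × [1 − Φ(1.96/√DEFF)].

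Example with m = 25 and ρ = 0.05: DEFF = 1 + 24 × 0.05 = 2.20; √2.20 = 1.48; 1.96/1.48 = 1.32; size = 0.186. A nominal p of 0.01 becomes about 0.08.

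| m | ρ | DEFF | CI factor | True size |
|---|---|---|---|---|
| any | 0 | 1.00 | 1.00 | 0.050 |
| 10 | 0.01 | 1.09 | 1.04 | 0.060 |
| 10 | 0.05 | 1.45 | 1.20 | 0.104 |
| 10 | 0.10 | 1.90 | 1.38 | 0.155 |
| 25 | 0.01 | 1.24 | 1.11 | 0.078 |
| 25 | 0.05 | 2.20 | 1.48 | 0.186 |
| 25 | 0.10 | 3.40 | 1.84 | 0.288 |
| 50 | 0.01 | 1.49 | 1.22 | 0.108 |
| 50 | 0.05 | 3.45 | 1.86 | 0.291 |
| 50 | 0.10 | 5.90 | 2.43 | 0.420 |

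**Simulation check.** D_ij = u_j + e_ij with true mean change 0, equal site sizes and 5,000 runs per scenario. With 15 sites of 25 patients, the paired t-test rejected in 0.047, 0.078, 0.190 and 0.282 of runs at ρ = 0, 0.01, 0.05 and 0.10. With 4 sites of 25 it rejected in 0.058, 0.082, 0.193 and 0.281, so the number of sites hardly matters. A t-test on site means rejected in 0.043 to 0.054 across all simulated scenarios.

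**Few sites.** A site-level test with 15 to 20 sites has a critical value of 2.14 to 2.09, close to 1.96. With 3, 4 or 5 sites it is 4.30, 3.18 or 2.78. Between-site variance is also poorly estimated there. With 3 sites of 25 patients, the ANOVA estimate is zero or negative in about 35% of samples at ρ = 0.05 and about 48% at ρ = 0.02. A valid test within a practice cluster therefore has little precision to offer.

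**The case against.** **The inflation is conditional.** It needs a positive ICC of the change score, and no document gives one. At ICC 0 the test is correct; at 0.01 with 25 patients per site its size is only about 8%. A reader might infer that the p-values are in fact too small. The documents do not support that; they support only that they may be. This objection stands.

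**The target of inference matters.** Sites are chosen on purpose, and Protocol 5.2.3 concedes that they may not represent US practice. If the target is the mean change at the enrolled sites alone, the paired t-test is not anti-conservative. Its standard error then slightly overstates the uncertainty, and at ρ = 0.10 its size is about 2 × [1 − Φ(1.96/√0.90)] = 0.039. This also stands as a condition. However, p-values labelled by practice type invite a reading beyond the enrolled sites, and the SAP does not say which target is meant.

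**The SAP states no interval for Table 15.** Correct. The 95% CIs are in Protocol 5.1.2, without a method, so the point about narrow intervals applies only if they are built from independent patients.

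**The objective is exploratory.** There is no alpha, power or success criterion. Protocol 5.3 says that no inferential statistics will be done, although SAP 2.1 limits this to the primary endpoint. No confirmatory claim rests on Table 15.

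**A larger issue remains.** Items 8 to 10 use 12-month recall at the initial visit and 3-month recall at follow-up, so the mean change need not be zero even if asthma is unchanged. A better standard error does not address this.

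**Two further inferences fail.** Table 15 is not the only inferential result for the secondary objectives, because SAP 5.1 also applies group tests to the ACE items. Nor are the touchpoint calls a source of site differences by design: they follow a common schedule and use the same questions (Protocol 4.1.13).

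**Conclusion.** The point holds in conditional form. Table 15 treats patients' changes as independent, nothing visible in the SAP accounts for site, and the program is delivered by site. If changes correlate within site and the inference is to sites beyond those enrolled, the p-values may be too small, and CIs built the same way may be too narrow. Over an assumed ICC of 0.01 to 0.10 and 10 to 50 followed patients per site, the true size of a nominal 5% test runs from about 6% to 42%. These figures rest on assumed inputs, equal site sizes and a true mean change of zero. They describe the calibration of the test and do not predict what the data show.

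One part needs no ICC: the by-site change and the 95% CIs that the protocol planned are absent from SAP 5.1.2, and Appendix B does not record their removal. The correction is cheap and makes the error bars more honest; it does not rescue or overturn a confirmatory finding.

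**What to change.** **Overall result.** In SAP 5.1.2, report mean AIRQ change with a 95% CI from an intercept-only model of the change with a random site intercept and small-sample degrees of freedom, and report the observed ICC. Small-sample-corrected cluster-robust standard errors are an acceptable alternative, but choose one method in advance: methods can weight sites differently when sizes are unequal and so target different means. The simulation covered only a site-mean t-test with equal sites, not this model.

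**Timing.** Appendix B is written in the past tense. If Table 15 has already been run, keep it and present the site-aware result beside it as a labelled sensitivity analysis.

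**Within practice clusters.** Show n, mean change and SD by site and by practice cluster, without p-values. Appendix B refers to the novel site in the singular; if that cluster is one site, between-site variation there cannot be estimated at all.

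**By-site display.** Restore the by-site change and the 95% CIs planned in Protocol 5.1.2. A patient-level CI is adequate for a single site, since it describes that site only.

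**Cost.** SAP wording and a few lines of code; the sites are known for every patient. The downside is wider intervals and less significant p-values. The change in recall period between visits needs its own caveat.

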5.1.3 Exploratory Objective(s): CCI

CCl

6. BIAS

6.1 Methods to Minimize Bias

Given that completing the ACE Questionnaire is optional, the potential for response bias (e.g., patients who like the telehealth platform may be more inclined to complete the survey) may be introduced into this study. This will be noted when interpreting the results. Additionally, patients who have a follow-up assessment may be more severe than those who do not; thus, change scores may not be representative of the entire sample, which will also be noted when interpreting results.

6.2 Adjustment for Multiple Comparisons

Not applicable.

7. INTERIM ANALYSES

Not applicable.

Appendix A. Scoring Information

AIRQ®

The AIRQ® includes 10 questions with Yes/No responses. A total AIRQ® score is generated by summing the number of “Yes” responses. The scores for the AIRQ® range from 0–10. Patients with scores of 0 or 1 are considered “well-controlled,” patients with scores of 2–4 are considered “not well-controlled,” and patients with scores of 5–10 are considered “very poorly controlled.”

ACE

There are eight questions on the ACE with Likert scale responses (Strongly Agree, Agree, Disagree, Strongly Disagree), and one open-ended question. There is no total score for the ACE. Scores for each individual item will be described by frequency.

NAEPP Step Coding

Code	Maintenance Therapy	Rescue therapy
Step 1	No daily medication checked	SABA alone with no maintenance therapy ^a
Step 2	Low-dose ICS	SABA with maintenance therapy ^b
	Theophylline Preparations	
	Leukotriene modifier	
	No daily medication checked	ICS+ SABA as rescue therapy alone Fixed dose combination fast-acting LABA/ICS alone as rescue
Step 3	Medium/High-dose ICS	For Steps 3 through 6, step assignment is based on maintenance therapy only.
	Low-dose ICS + LAMA	
	Low-dose ICS+ leukotriene modifier	
	Low-dose ICS + theophylline preparation	
	Low dose ICS + LABA	
Step 4	Medium-dose ICS/LABA	
	Medium dose ICS + LAMA	
	Medium/high dose ICS + theophylline	
	Medium/high dose ICS + leukotriene modifier	
Step 5	High-dose ICS/LABA + LAMA	
	High-dose ICS/LABA	
Step 6 ^c	Any maintenance therapy AND	Chronic oral systemic corticosteroids OR Biologic

^a Possible alternative: “SABA as rescue therapy via nebulizer without other rescue or maintenance therapies” or “Primatene Mist as rescue and no maintenance therapy”

^b Possible Alternative: “SABA as rescue therapy via nebulizer with other rescue maintenance therapies” or “Primatene Mist as rescue with maintenance therapy(s)”

Appendix B. Revisions to Select Analyses Initially Detailed in this SAP

Due to the nature of the data collected or to enhance clarity of presentation or interpretation of findings, some revisions were made to select analyses initially specified in the SAP. These revisions are detailed below:

- Novel site results were displayed in separate tables (N table series)
- All analyses by language were not conducted since the AIRQ was only administered in English language.
- There was no data on PRECISION education resource views/downloads for the specialty care cluster so tables 22c and 23c could not be run
- Some analyses could not be conducted due to the small sample size, e.g., for Tables 23e-23j, Tables 29b1-b3, Tables 29e-t, Table 30a, Table N4d, Tables N6b-N6i, Tables N7b-N7i, Table N8e, N10d, N22f, N23e, N29e-N29t or due to lack of data (i.e., no telehealth visits **CCI** or medical record history data available for the novel site so Table N3c, N4b, N4c, N5, N8d, N9b, N10b, N10c, N22e, N23e could not be presented).
- There was only one follow-up visit per patient so some analyses could not be presented (Table 24 and Table N24 series) or were modified (Table 25)
- Some tables duplicated content from other tables and are not presented (content for the Table 26, 27, N26 and N27 series can be found in the Table 20, 21, N20 and N21 series)
- Inferential statistical tests (e.g., ANOVA, chi-square test) were run to determine if differences between the practice clusters were statistically significant for Table 3e and Tables 8 series, Tables 10 series, Table 20 series
- A Bowker's test was used instead of a Cochran's Q test to evaluate if there were within-patient changes in OCS use (Table 31b) as the Cochran's Q test was not suitable 9 (only provides a method for testing three or more binary matched pairs).

Statistical analysis plan
D2287L00028 (EVA-26645)

AstraZeneca
27 Sep 2023

SIGNATURES

ASTRAZENECA SIGNATURES

D2287L00028 PRECISION Study 4 – Implementation

Statistical Analysis Plan for the Implementation of the US PRECISION AIRQ®,
Asthma Checklist, and Educational Resources (PRECISION Program) into
Clinical Practice Using Telehealth and In-Person Platforms: Addendum

This statistical analysis plan addendum has been subjected to an internal AstraZeneca review.

I agree to the terms of this statistical analysis plan.

AstraZeneca Study Statistician

PPD

Evidera Statistical Oversight

PPD

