4.3 Other Variables and Covariates

The sample will be characterized by practice cluster: (1) primary care sites (e.g., private practice, FQHC); (2) specialty care sites (pulmonary, asthma/immunology); and (3) novel sites (e.g., pharmacy, nurse practitioners, nurse educators, prescribers and non-prescribers, telehealth component of Allergy and Asthma Network).

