[REDACTED] [REDACTED] [REDACTED] [REDACTED] Descriptive statistics (n, %) will be presented for the ACE Questionnaire (item scores) by practice cluster, visit platform, AIRQ® control score, exacerbation history, education level, language, age, sex, and NEPP step level (Table 7 series). Item responses and scores on the patient-reported outcome measures (AIRQ®, CCI [REDACTED] and ACE) will be compared across groups (practice cluster, visit platform, exacerbation history, education level, language, age, sex and NAEPP step level). For continuous variables, ANOVA will be used to compare mean scores across groups; pairwise comparisons between means will be performed using Scheffe's test adjusting for multiple comparisons for more than two groups. For categorical data, chi-square analyses will be used to compare frequencies by groups. No adjustments will be made for multiple groups.

For the follow-up analysis dataset, a patient disposition table will be developed to descriptively characterize the follow-up analysis set in terms of age group, language, race, and education by practice cluster (Table 8a). The mean time to first follow-up visit will be described (n, %) in Table 8b. For the primary care and specialty clusters, the first follow-up clinical CRF will be completed at the patient's first follow-up visit. For the novel cluster sites where patients are receiving multiple asthma coaching sessions, the follow-up clinical CRF will be completed at their final coaching session.

Descriptive statistics (n, %) will be used to describe patients with a follow-up visit by AIRQ® control level at initial visit (Tables 8c). Descriptive statistics (n, %) will also be used to describe patients with a follow-up visit by exacerbation history, education level, language, age, sex, and NAEPP step level at the initial visit (Tables 8d to 8i). Descriptive statistics (n, %) will be used to describe patients with a follow-up visit by HCP actions at the initial visit overall and by practice cluster (Table 8j to 8m).

Clinical characteristics and visit information from the first follow-up visit will be presented using descriptive statistics (n, mean [SD], median, range) (Tables 9a to 9e). Descriptive statistics (n, mean [SD], median, range) will also be used to present the results (overall and by practice cluster) for the first follow-up AIRQ® scores and control levels (Table 10a). AIRQ® scores from the first follow-up

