visit will also be summarized by visit platform (telehealth vs. in-person), exacerbation history, education level, language, age, sex and NAEPP step level (Table 10b to 10h). In Table 10i, descriptive statistics (mean, SD, median, range) will be used to detail the average number of AIRQs® completed by patients overall and in each practice cluster. In Table 10j, AIRQ® scores from the patient's final follow-up (if more than 1 follow-up AIRQ) will be summarized.

5.1.1 Primary Objective: Assess the Process and Potential Benefits of Implementing the AIRQ™, Asthma Checklist, and Educational Resources (PRECISION Program) into Clinical Practice

This analysis will be conducted on the HCP analysis set of clinicians who completed the post-study survey. Descriptive statistics (n, %) will be used to summarize the proportion of responses for each of the categorical items on the post-study survey (e.g., How would you rate the overall ease of implementing the AIRQ™ into your clinical practice using the telehealth platform?). Descriptive statistics (mean [SD], median, range) will be used to summarize the number of patients treated using the PRECISION program (Table 11). Results will be presented overall and by practice cluster.

Qualitative analyses will be conducted to evaluate the frequency of descriptive free-text responses to open-ended questions on the post study survey (e.g., What features of the PRECISION program do you think could be improved?) (Table 12 series), from the qualitative interviews with key site staff and clinicians (Table 13 series), and from the implementation touchpoint calls with key site staff and clinicians (Table 14 series).

5.1.2 Secondary Objective(s): 1) To Assess Patient Visit Satisfaction When the AIRQ™ Is Initiated as Part of a Telehealth or In-Person visit with Their HCP; 2) To explore change in AIRQ® scores from the initial visit to follow-up visit(s)

To assess patient satisfaction with AIRQ®, descriptive statistics (n, %) will be used to summarize patient responses to the ACE Questionnaire overall and by practice cluster (Table 7a). Scores will also be summarized by visit platform (in-person vs. telehealth), AIRQ® control level, education level, age, exacerbation history, and patient language (Table 7 series).

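### Practice clusters are tested on follow-up AIRQ without the initial AIRQ, so differences present at entry can show up as significant differences at follow-up

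*SAP*

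**What the plan says.** SAP Appendix B adds significance tests between practice clusters: "Inferential statistical tests (e.g., ANOVA, chi-square test) were run to determine if differences between the practice clusters were statistically significant". It lists where this was done: one baseline table (3e) and the whole of the 8, 10 and 20 series. SAP 5.1 defines the Table 10 series. Table 10a gives results "overall and by practice cluster) for the first follow-up AIRQ® scores and control levels (Table 10a"), and Tables 10b to 10h break the same follow-up scores down by other patient and visit characteristics.

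The form of test for scores is also in SAP 5.1: "For continuous variables, ANOVA will be used to compare mean scores across groups", with Scheffe pairwise comparisons and chi-square for categories. SAP 4.3, the section on covariates, names only the cluster itself: "The sample will be characterized by practice cluster".

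The initial AIRQ is used elsewhere. Table 4a shows it by cluster. Table 8c describes followed patients by initial control level, and Appendix B says the Table 8 series was tested between clusters. In SAP 5.1.2, change to first follow-up "will be evaluated using paired t-tests for the overall sample, and by practice cluster (Table 15"), and Tables 16 to 19 give shifts in control level. The follow-up set (SAP 3) is made up of patients who completed the initial AIRQ and "have at least one follow-up visit completed in the nine-month implementation period" with a follow-up AIRQ.

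**The concern.** Secondary objective 2 (SAP 1.2) is about change in AIRQ from the initial visit. Among the visible analyses, change is tested only within each cluster, while the significance test between clusters is on the raw follow-up level. The two do not combine into an answer about whether clusters changed differently.

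Primary care, specialty and novel sites may see patients with different asthma control at entry. If so, part or all of that difference carries over to follow-up through the correlation between a patient's two scores. A small p-value in Table 10 could then reflect who was enrolled, yet be taken as evidence that the program did better in one type of practice. The bias sections (Protocol 5.2.1, SAP 6.1) discuss selection into follow-up but not entry differences between clusters.

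**Working it through.** The documents give no SD, correlation, alpha, power or follow-up count for this comparison, so there is no planned figure to reproduce.

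**Inputs**
- Score range 0 to 10 (SAP Appendix A).
- Cluster size: 3 to 5 sites (Protocol 5.3) at about 50 patients gives 3 × 50 = 150 to 5 × 50 = 250 enrolled per cluster. Follow-up is optional and its number is not given; 50 to 150 followed per cluster is assumed.
- Assumed: SD 2.5; correlation r between initial and follow-up AIRQ 0.3 to 0.7; initial gap g between clusters 0 to 1.5 points; two-sided 5% level.
- Two clusters are compared. Appendix B puts the novel sites in separate tables, so the main contrast is probably primary care against specialty care (an inference).

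**Formula.** If cluster has no effect once the initial score is known, the expected follow-up gap is d = r × g. With SE = 2.5 × √(2/n),

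P(significant) = Φ(d/SE − 1.96) + Φ(−d/SE − 1.96).

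Example: n = 100, r = 0.5, g = 1. Then d = 0.5, SE = 2.5 × √0.02 = 0.354, d/SE = 1.41, and P = 29%.

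| Initial gap | Range over n = 50–150, r = 0.3–0.7 | n = 100, r = 0.5 |
|---|---|---|
| 0 | 5% | 5% |
| 0.5 | 6–23% | 11% |
| 1.0 | 9–68% | 29% |
| 1.5 | 15–95% | 56% |

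If instead the initial gap persists in full (both clusters change by the same mean amount), d = g, and the ranges become 17–41%, 52–93% and 85–99.9% for gaps of 0.5, 1.0 and 1.5.

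**Simulation of the candidate remedies** (1,000 runs per cell, scores rounded and held to 0–10, gap 1, r = 0.5; share of runs significant):

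| Truth | n per cluster | Unadjusted | ANCOVA on initial AIRQ | ANOVA of change |
|---|---|---|---|---|
| No cluster effect given initial score | 50 | 16% | 6% | 20% |
| | 100 | 28% | 6% | 31% |
| | 150 | 39% | 4% | 43% |
| Initial gap persists, equal mean change | 50 | 47% | 19% | 5% |
| | 100 | 79% | 35% | 4% |
| | 150 | 91% | 51% | 4% |

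Each remedy holds about 5% under its own definition of no cluster difference and not under the other's. The unadjusted test holds it under neither once there is an initial gap.

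**The case against.** The strongest reply is that the unadjusted test is valid for its literal question, whether mean AIRQ at follow-up differs between clusters. The study is descriptive, Table 10 sits among general summaries, and no visible passage claims a different program effect by cluster. A reader can also check entry status in Tables 4a and 8c and see change and shifts in Tables 15 to 19. All of this stands. The fault lies in what the p-value invites, not in the test itself. Those tables do not replace a comparison between clusters, because separate paired tests within clusters do not test whether the changes differ.

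Some stronger readings are tempting, and the documents do not support them:
- A reader might infer that clusters will be reported as different. That needs an initial gap, and the documents give neither a gap nor a correlation or follow-up count. With no gap the rate is 5%.
- A reader might infer that Table 15 is the only use of the initial score. Tables 16 to 19 use it too.
- A reader might infer that no adjusted cluster analysis exists anywhere. SAP 5.1.3 and the exploratory outcomes are redacted, so that cannot be confirmed. An adjusted model there would still leave the Table 10 tests as described.
- A reader might infer that ANCOVA would remove the bias. The simulation shows that it does not if the initial gap simply persists.

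**Conclusion.** The point holds as a limit on interpretation with an inexpensive remedy. The Table 10 cluster tests, as described, ignore an initial score that every followed patient has, and no visible analysis compares clusters on change or adjusted follow-up. Initial differences can therefore surface as significant follow-up differences. The chance is 5% with no initial gap, 6% to 23% at 0.5 points and 9% to 68% at 1 point, if cluster has no effect given the initial score, and higher if the gap persists in full. These figures rest on the assumed SD, correlation, sample size and 5% level, and show the possible scale rather than what happened in this study. This concerns a secondary, descriptive analysis and does not touch the primary objective.

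**What to change.** For the between-cluster comparisons of follow-up AIRQ score and control level:

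1. Add an ANCOVA of follow-up AIRQ on cluster plus the patient's initial AIRQ. For control level, use ordinal logistic regression with initial control level as covariate. Report adjusted differences or odds ratios with 95% confidence intervals.
2. Add a comparison of mean AIRQ change between clusters, with 95% confidence intervals.
3. Keep the raw Table 10 means, and label their p-values as unadjusted and descriptive.
4. Leave Table 10i (number of AIRQs completed) out of this, since the adjustment has no meaning there.

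The cost is a few sentences in the SAP and a re-run on data already held. Because Appendix B describes tests already carried out, the additions should be marked as post hoc.

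The downside should be stated with the results. In non-randomised groups the two analyses answer different questions and may disagree. Residual confounding and selection into follow-up remain. Items 8 to 10 ask about 12 months at the initial visit and 3 months at follow-up, so the initial and follow-up scores are not the same measure.
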